3.4.5 Patient localization and immobilization

1. The CT or MR simulation will occur with the patient supine position in a frameless thermoplastic head mask.
2. The treatment planning software will be used to generate the isocenter position information
3. Accurate positioning is achieved by matching an in-room cone-beam CT (CBCT) to the planning CT (PCT) using a 6 DOF rigid registration method customized to use mutual information metric in Mattes's formulation. In addition to couch shifts, the 6 DOF-registration calculates the spin, tilt, and couch angles required for precise target positioning. The spin and tilt are applied using a customized couch mount while couch translations and rotation are applied using the treatment console. A second CBCT is acquired to verify positioning with the clinical system before treatment delivery²⁰.

3.4.6 Dose Limitation to Critical Structures

1. In addition to the above defined GTVs, CTVs and PTVs, both eyes, the lenses of both eyes, the optic nerves, the optic chiasm, the brainstem and the spinal cord and the whole brain and normal brain parenchyma will be contoured. Normal brain is defined as the whole brain minus the GTV. Dose-volume histograms will be generated and whole organ dose and maximum point dose will be recorded for each critical structure.
2. If the patient has received no prior cranial irradiation, the maximal point doses permissible to the structures from the current radiation therapy plan are listed below* (Table 2).

3. If the patient has received previous WBRT, the previous dose received to critical structures should be obtained or a representative dose distribution file should be simulated. This dose should then be converted to BED (assuming an alpha-beta ratio of 3 for late effects) and added to the BED to the critical structures from the current treatment plan. This sum BED must meet the cumulative dose constraint below[¶] (Table 2). No adjustments for time between previous radiation treatment will be made for the purpose of this protocol.
4. If a patient is recommended to receive whole brain radiation after completion of the study treatment, the constraints listed in Table 3 should be met during the whole brain radiation treatment. It is recommended that the 90% isodose volume from the hypofractionated radiosurgery treatment be created into an avoidance structure and constrained such that the maximum dose to this structure or the normal brain has a cumulative BED₃ of ≤ 150 (equivalent to max dose 15-18 Gy when delivered in 3-3.5 Gy per fraction).

Table 2. Normal Tissue Constraints for Hypofractionated Radiosurgery Treatment

Cumulative BED ₃	Volume	No Previous RT*	Previous RT [¶]
		Maximum Dose	Maximum Cumulative BED ₃
Brainstem	Max, $\leq 0.03\text{cc}$	26 Gy	90
Spinal Cord	Max, $\leq 0.03\text{cc}$	22 Gy	75
Eye (Globe), each	Max, $\leq 0.03\text{cc}$	20 Gy	66
Lens, each	Max, $\leq 0.03\text{cc}$	2.5	12
Optic Nerve, each	Max, $\leq 0.03\text{cc}$	26 Gy	90
Optic Chiasm	Max, $\leq 0.03\text{cc}$	26 Gy	90
Normal Brain	Modal	20 Gy	15 Gy
Normal Brain	$\leq 23\text{ cc}$	4 Gy/fraction	4Gy/fraction

Table 3: Constraints for Whole Brain Radiation following hypofractionated radiosurgery

Cumulative BED ₃	Volume	WBRT after study treatment
		Maximum Cumulative BED ₃
Brainstem	Max, $\leq 0.03\text{cc}$	90
Spinal Cord	Max, $\leq 0.03\text{cc}$	75
Eye (Globe), each	Max, $\leq 0.03\text{cc}$	66
Lens, each	Max, $\leq 0.03\text{cc}$	12
Optic Nerve, each	Max, $\leq 0.03\text{cc}$	90
Optic Chiasm	Max, $\leq 0.03\text{cc}$	90
Dose within 90% isodose line from study treatment or within normal brain	Max, $\leq 0.03\text{cc}$	150

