In our own experience at Emory¹⁹ with 47 patients receiving HR for both solid intact metastasis (22) and resection cavities (25), we have demonstrated 6 month and 1 year LC rates of 69% (CI 0.62-0.77) and 59% (CI 0.67 – 0.50), with 3 (6.4%) patients experiencing symptomatic radiation necrosis. On multivariate Cox-regression analysis, improved local control was associated with smaller planned target volume (PTV) volume (SS, $p=0.02$) and higher dose per fraction (NS, $p=0.06$). No significant association was found between LC and previous RT received, resection cavity vs. solid tumor, total dose, biological equivalent dose (BED) or single fraction equivalent dose (SFED). These results show HR is well tolerated in both new and recurrent, previously irradiated large intact or resected brain metastases. Significantly higher rates of local failure are observed with larger PTV volumes suggesting a need for dose escalation when using HR for large intracranial lesions.

We propose a prospective phase I trial for patients with solid brain metastasis greater than 3cm and less than 6 cm, who have either had no treatment or who are status post surgical resection. The purpose of this trial will be to determine the maximum tolerated dose for fractionated radiosurgery delivered in 5 fractions with a minimum of 2 and a maximum of 3 fractions being delivered per week. Results from this trial may form the basis of future trials evaluating the efficacy of fractionated radiosurgery regimens for local and distant control of brain metastasis and for directly comparing WBRT with FRS, for patients not amenable to single fraction SRS. Such a phase III study would answer the question about as to whether local irradiation is adequate treatment for patients with large brain metastasis.

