3.2 Enrollment/Randomization

This study will include 8 patient cohorts with 3 patients per cohort. The patients will be enrolled and treated following a Bayesian method permitting precise determination of the therapeutic working-dose while directly controlling the likelihood of an overdose. The method, known as Escalation with Overdose Control (EWOC), has been used to design phase I clinical trials at several cancer centers including the Fox Chase Cancer Center (PA), the Sylvester Comprehensive Cancer Center (FL), and the Winship Cancer Institute (GA) and pharmaceutical companies. EWOC was the first dose-finding procedure to directly incorporate the ethical constraint of minimizing the chance of treating patients at unacceptably high doses. Its defining property is that the expected proportion of patients treated at doses above the MTD is equal to a specified value α , the feasibility bound. This value is selected by the clinician and reflects his/her level of concern about overdosing.

The dose levels for the trial are summarized in Table 1. The dose for the first cohort of 3 patients in the trial will be the dose level 0, previous results indicating this to be a safe dose. The patient accrual will be suspended until the 4 month toxicity evaluation is completed for all previously enrolled patients. The dose for each subsequent cohort of 3 patients will be determined so that, on the basis of all available data and the target highest acceptable toxicity level of 25% DLT, the probability that it exceeds the MTD is equal to a pre-specified value α . In this trial, we set $\alpha = 0.25$ and increase α in small increments until $\alpha = 0.5$, this value being a compromise between the therapeutic aspect of the agent and its toxic side effects. The dose selected for every patient in the trial will be between the minimum dose of 27.5 Gy and the maximum allowable dose of 40 Gy. The trial will be terminated if 3 DLTs are observed in any cohort of 3 patients treated with the lowest dose level. The trial will stop after 24 patients have been enrolled and MTD will be estimated from one of the 6 specified dose levels listed in the Table 1. If no MTD is found because even the highest dose level is still considered under toxic, then the highest dose group will be considered the MTD and expanded to 12 patients.

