3.4.2 Target Volume Determination

1. Target volume and isocenter determination will be based on a simulation CT and/or treatment planning MRI (with and without contrast)
2. Stereotactic CT scan slice thickness may not exceed 1 mm
3. Treatment planning MRI slice thickness may not exceed 2 mm
4. The gross target volume (GTV) will include the entirety of the MRI defined T1 post contrast enhancing brain metastasis or the resection cavity including any residual enhancing disease. Surrounding areas of edema will not be considered part of the target volume.
5. A margin of 0.5 mm in all directions will be applied to the GTV to create the clinical target volume (CTV)
6. An additional margin of 1 mm will be added to the CTV to create the PTV.
7. Target volumes (in cc) will be determined for the GTV, CTV and PTV using the treatment planning software

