3.4.4 Dose prescription and dosimetry requirements

1. Dose will be prescribed to the isodose line that encompasses the entirety of the PTV.
 1. If intensity modulated radiosurgery (IMRS) is utilized, standard prescription isodose is to 98% (range 95-100%)
 2. If dynamic conformal arcs (DCA) are utilized, standard prescription isodose is to 80% (range 70-90%).
 3. If gamma knife is utilized, standard prescription isodose is to 50%

2. Doses are specified such that at least 95% of the PTV shall receive 100% of the prescribed dose.
 3. Inhomogeneity within the PTV should be kept within $\pm 10\%$ of the prescribed dose, and the minimum dose PTV should be kept within 10% of the dose at the isocenter.
 4. The marginal dose and the 100% dose (isocenter dose) will be recorded for each patient.
 5. For quality control, representative isodose lines (eg. 20%, 40%, 60%, 80%, 90%) must be generated for each patient.
- Quality of PTV coverage will be categorized according to selected isodose line:
1. Total – selected isodose line completely encompasses the PTV
 2. Marginal – selected isodose line incompletely encompasses the PTV, but not by more than 10% of the PTV volume.
 3. Subtotal - selected isodose line incompletely encompasses the PTV, but by more than 10% of the PTV volume. This will not be accepted.
6. Conformality index requirements (ratio of prescription isodose volume to the target volume (PI/TV))
 1. Per protocol if between 1.0 and 2.0
 2. Acceptable variation if ≥ 0.9 but < 1.0 or > 2.0 but ≤ 3.5 .
 3. Unacceptable deviation if > 3.5 .

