4.0 PATIENT SELECTION

4.1 Inclusion Criteria

- 4.1.1 Pathologic proven diagnosis of solid tumor malignancy.
- 4.1.2 Age ≥ 18 .
- 4.1.3 One brain metastasis or brain metastasis resection cavity with maximal diameter ≥ 3 cm (or ≥ 14 cc.) and ≤ 6 cm (or ≤ 113 cc.).
- 4.1.4 RPA class I-II/ Karnofsky Performance Status $\geq 70\%$ (See **Appendix D for definitions**)

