4.2 Exclusion Criteria

- 4.2.1 Prior SRS to adjacent lesion such that planning target volume would have received more than 12 Gy
- 4.2.2 RPA class III (KPS < 70%, see **Appendix D definitions**).
- 4.2.3 Brain metastasis or resection cavity volume < 3 cm or 14 cc. or > 6cm or 113 cc.
- 4.2.4 Radiosensitive or non-solid (eg. small cell lung carcinomas, germ cell tumors, leukemias, or lymphomas) or unknown tumor histologies.
- 4.2.5 Concurrent chemotherapy (no chemotherapy starting 14 days before start of radiation).
- 4.2.6 Evidence of leptomeningeal disease by MRI and/or CSF cytology.
- 4.2.7 Current pregnancy
- 4.2.8 More than 8 weeks between resection and radiosurgical procedure
- 4.2.9 Metastases to brain stem, midbrain, pons, or medulla or within 5 mm of the optic apparatus (*optic nerves and chiasm*).
- 4.2.10 Inability to undergo MRI evaluation for treatment planning and follow-up

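### For large, roughly spherical lesions surrounded by brain, the eligible size range, target margins, conformality range and Table 2 normal-brain limit do not fit together, and the misfit grows with dose level

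*Combined protocol and SAP*

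**What the plan says.** - **Eligibility.** Section 4.1.3 admits "One brain metastasis or brain metastasis resection cavity with maximal diameter" from 3 cm (or 14 cc) to 6 cm (or 113 cc). Section 4.2.3 excludes "Brain metastasis or resection cavity volume < 3 cm or 14 cc. or > 6cm or 113 cc".
- **Margins.** Section 3.4.2 expands the GTV by 0.5 mm to form the CTV, and "An additional margin of 1 mm will be added to the CTV to create the PTV". The total is 1.5 mm.
- **Prescription.** Section 3.4.4 prescribes to the isodose enclosing the PTV and requires at least 95% of the PTV at full dose. On the conformality index (prescription isodose volume over target volume) it says "Per protocol if between 1.0 and 2.0".
- **Dose.** Section 3.2 keeps every patient "between the minimum dose of 27.5 Gy and the maximum allowable dose of 40 Gy". Over five fractions that is 5.5 to 8 Gy per fraction, as in Table 1.
- **Normal-brain limit.** Section 3.4.6 item 1 says "Normal brain is defined as the whole brain minus the GTV". One Table 2 row sets 23 cc at 4 Gy per fraction. The figure is the same with and without previous radiation and is not varied by dose level.
- **Rationale.** Section 1.0 says "Significantly higher rates of local failure are observed with larger PTV volumes suggesting a need for dose escalation".

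The documents do not say what follows if a plan misses the normal-brain limit.

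**The concern.** Normal brain is everything outside the GTV, so the margin shell uses up part of the 23 cc before dose has begun to fall off. The shell grows with lesion size while the 23 cc stays fixed. The 4 Gy per fraction threshold is also fixed, so each escalation step leaves more dose to lose over the same distance.

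The primary endpoint is the MTD, sought for lesions between 3 and 6 cm, and failure in large volumes is the stated reason to escalate. If the limit is enforced by leaving patients out, the upper dose levels would be tested in smaller lesions than the MTD is stated for. If it is not enforced, large lesions are treated outside the protocol's own limit.

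The plan does not say which applies. Under 3.1 patients enter a dose group at enrolment. The last item of 3.4.1 asks only for a quality check before treatment is completed. The replacement rule in 3.2 and 5.2 covers only patients who miss the 4-month assessment because of a toxicity judged unrelated to treatment. Neither the dose-finding rule in 3.2 nor the strata in 5.3.3 use lesion volume.

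**Working it through.** **Inputs.** Diameter d from 3 to 6 cm (4.1.3); margin 0.15 cm per side (3.4.2); limit 23 cc at 4 Gy per fraction outside the GTV (3.4.6); prescription 5.5 to 8 Gy per fraction (Table 1). I read the Table 2 row as allowing at most 23 cc of normal brain at or above 4 Gy per fraction.

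**The plan's own figures.** With V(d) = πd³/6, V(3) = 14.1 cc and V(6) = 113.1 cc. These match the 14 and 113 cc in 4.1.3, so the eligibility limits treat lesions as spheres. I do the same, with the lesion wholly surrounded by brain.

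**Step 1: shell and remaining room.** GTV = V(d); PTV = V(d + 0.3); shell = PTV − GTV. The rim f left beyond the PTV solves V(d + 0.3 + 2f) = GTV + 23.

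| d (cm) | GTV (cc) | PTV (cc) | Shell (cc) | 23 − shell (cc) | Rim f (mm) |
|---|---|---|---|---|---|
| 3 | 14.1 | 18.8 | 4.7 | 18.3 | 4.2 |
| 4 | 33.5 | 41.6 | 8.1 | 14.9 | 2.3 |
| 5 | 65.4 | 78.0 | 12.5 | 10.5 | 1.1 |
| 6 | 113.1 | 130.9 | 17.8 | 5.2 | 0.4 |

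The margin alone never breaks the limit. At 95% PTV coverage a 6 cm lesion has a prescription volume of 0.95 × 130.9 = 124.4 cc. That leaves 136.1 − 124.4 = 11.7 cc, a rim of about 0.9 mm.

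**Step 2: conformality, with no fall-off counted.** Normal brain inside the prescription isodose = index × PTV − GTV. The highest index that keeps it within 23 cc is (GTV + 23)/PTV:
- 3 cm: 37.1/18.8 = 1.97
- 4 cm: 56.5/41.6 = 1.36
- 5 cm: 88.4/78.0 = 1.13
- 6 cm: 136.1/130.9 = 1.04

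An index of 2.0 gives 23.5 cc at 3 cm. An index of 1.5 exceeds 23 cc above 3.65 cm, and 1.2 above 4.60 cm. This step needs no assumed dose gradient.

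**Step 3: dependence on dose level.** The 4 Gy line, as a share of prescription, is 4/5.5 = 73% (level -1), 4/6 = 67% (level 0), 4/6.5 = 62%, 4/7 = 57%, 4/7.5 = 53% and 4/8 = 50% (level 4). The rim in Step 1 does not change with dose, so the requirement tightens at each level.

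**Step 4: how much of the range is affected (fall-off assumed).** The documents give no gradient. The largest sphere that complies, by assumed distance from PTV edge to the 4 Gy per fraction line:

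| Distance | Wholly within brain | 30% of shell outside brain |
|---|---|---|
| 1 mm | 5.2 cm | 6.2 cm |
| 2 mm | 4.2 cm | 5.1 cm |
| 3 mm | 3.6 cm | 4.4 cm |
| 4 mm | 3.1 cm | 3.8 cm |
| 5 mm | 2.7 cm | 3.3 cm |

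To show the effect of dose level, assume exponential fall-off that halves dose in h mm, so the distance is h × ln(D/4)/ln 2 for D Gy per fraction. For spheres within brain, the largest compliant diameter at 30, 35 and 40 Gy is 4.97, 4.53 and 4.22 cm (h = 2); 4.41, 3.92 and 3.58 cm (h = 3); 3.98, 3.45 and 3.08 cm (h = 4).

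**The case against.** **Fall-off, shape and depth are not given.** A reader might infer that the limit cannot be met for most of the 3 to 6 cm range. The documents do not support that. If dose halves in 2 mm, only about a third of the diameter range fails at 30 Gy. If half the shell lies outside brain and dose halves in 3 mm, lesions comply up to 6.4 cm at 30 Gy and 5.25 cm at 40 Gy. A 6 × 3 × 3 cm ellipsoid is eligible by diameter, measures 28 cc and leaves 2.5 mm rather than 0.4 mm. A share of the diameter range is also not a share of patients, and no size distribution is given. All of this stands. The shape argument works only because such a lesion is small in volume: for a given volume the sphere has the least surface, and eligibility runs to 113 cc.

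**The conformality range is an allowance, not a target.** A plan can be tighter than 2.0, and the stricter limit governs. That is fair, and there is no logical contradiction. What remains is that a plan can be graded per protocol in 3.4.4 and still miss Table 2, with no text linking the two.

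**The effect on the MTD is inference.** A reader might infer that dose level is confounded with lesion volume whether or not the limit is enforced. That goes too far: without enforcement, nothing in the plan ties volume to dose level. Confounding follows only if the limit is enforced by exclusion, which no section states. Protocol violations are reported to the investigators under 7.2.3, but the handling of such patients in dose-finding is still unstated.

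**Conclusion.** The concern holds in a limited form. For large, roughly spherical lesions surrounded by brain, sections 4.1.3/4.2.3, 3.4.2, 3.4.4 item 6 and the Table 2 normal-brain row do not fit together, and the fit worsens with each dose level. The firm part uses document figures plus spherical geometry within brain: index ceilings falling from 1.97 at 3 cm to 1.04 at 6 cm, and 0.4 to 0.9 mm left for fall-off at 6 cm. The extent is uncertain: with 1 to 5 mm assumed to the 4 Gy per fraction line, the largest compliant sphere runs from 5.2 down to 2.7 cm, or 6.2 down to 3.3 cm with 30% of the shell outside brain.

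The consequence for the MTD is conditional on how the limit is applied. That the plan does not say is a fact. This is worth correcting, with moderate confidence. It does not by itself show that the dose-finding is invalid.

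**What to change.** 1. Reconcile 4.1.3/4.2.3, 3.4.4 item 6 and the Table 2 normal-brain row. Which of them changes is for the investigators.
2. State in 3.2 and 5.2 how a patient whose plan misses the normal-brain limit is handled and counted in the dose-finding.
3. Add to 5.3 a table, by dose level, of the GTV and PTV volumes already recorded under 3.4.2 item 7 and of compliance with the normal-brain limit.
4. Limit the stated MTD to the lesion volumes actually treated at that level.

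Requiring a compliant plan at the open level before a patient counts is not advised. It would be a clinical eligibility rule, and it would itself select smaller lesions at higher levels.

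The cost is a protocol amendment and an added analysis table, with no extra patients or procedures. The downside is that the MTD claim may cover a narrower size range.

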5.3 Statistical Analysis

5.3.1 Primary Analysis: The rate of toxicities at 4 months will be calculated with 95% confidence interval (CI).

5.3.2 Secondary Analysis:

5.3.2.1 The median time to local/distant brain progression will be calculated by Kaplan-Meier method with 95% CI. For a given time point, say 4 month, the rate of local/distant progression will be calculated with 95%CI.

5.3.2.2 The median of OS time with 95% CI will be calculated by Kaplan-Meier method.

5.3.2.3 Neurocognitive effect and QOL outcomes will be regressed over time using GEE model. The population change over time (slope) will be estimated with 95%CI.

5.3.3 Patient Stratification: All enrolled patients will proceed through dose escalation as a single cohort, however patients will be analyzed as separate strata, should enrollment allow it, based on the following criteria.

5.3.3.1 Intact brain metastasis versus resection cavity.

5.3.3.2 No previous cranial irradiation versus previous WBRT or other cranial irradiation.

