APPENDIX E

Eligibility Checklist

1. _____ Pathological proven diagnosis of solid tumor malignancy, not a radiosensitive or non-solid (eg. small cell lung carcinomas, germ cell tumors, leukemia, or lymphoma) or unknown tumor histology.
2. _____ Age ≥ 18 .
3. _____ One brain metastasis or brain metastasis resection cavity with maximal diameter greater $\geq 3\text{cm}$ (or $\geq 14\text{ cc.}$) and $\leq 6\text{cm}$.
4. _____ RPA class I-II/ Karnofsky Performance Status $\geq 70\%$ (See **Appendix D for definitions**)
5. _____ No Prior SRS to adjacent lesion such that planning target volume would have received more than 5 Gy
7. _____ No concurrent chemotherapy (no chemotherapy starting 14 days before start of radiation).
8. _____ No evidence of leptomeningeal disease by MRI and/or CSF cytology.
9. _____ Negative serum or urine pregnancy test within 4 weeks of enrollment
10. _____ Less than or equal to 8 weeks between resection and enrollment
11. _____ No metastases to brain stem, midbrain, pons, or medulla or within 5 mm of the optic apparatus (*optic nerves and chiasm*).
12. _____ Patient is able to undergo MRI evaluation for treatment planning and follow-up

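### Section 3.4.6 states no critical-structure rule for patients with prior SRS or other focal cranial radiotherapy, and the Table 2 column they would use can allow the brainstem more study dose than in a never-irradiated patient

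*Combined protocol and SAP*

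**What the plan says.** Two conditional rules in section 3.4.6 govern dose to critical structures. Item 2 opens: "If the patient has received no prior cranial irradiation, the maximal point doses permissible to the structures from the current radiation therapy plan", and refers to Table 2. Item 3 opens: "If the patient has received previous WBRT, the previous dose received to critical structures should be obtained". It then converts that dose to BED with an alpha-beta ratio of 3, adds the BED of the study plan, and says "This sum BED must meet the cumulative dose constraint below".

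Table 2 has two limit columns:

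- *No Previous RT* gives a maximum dose for the study plan: 26 Gy for brainstem, optic nerve and chiasm, 22 Gy for spinal cord, 20 Gy for globe and 2.5 (no unit printed) for lens.
- *Previous RT* gives a maximum cumulative BED3 for the same organs: 90, 75, 66 and 12. Its two normal-brain rows are instead printed in Gy: 15 Gy modal (20 Gy without prior RT) and 4 Gy per fraction (the same in both columns).

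On eligibility, 4.2.1 excludes "Prior SRS to adjacent lesion such that planning target volume would have received more than 12 Gy". The Appendix E checklist puts the threshold lower: "No Prior SRS to adjacent lesion such that planning target volume would have received more than 5 Gy". Under either figure, prior SRS that gave the planning target volume less than the threshold is allowed. Section 5.3.3.2 plans a stratification by "No previous cranial irradiation versus previous WBRT or other cranial irradiation".

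**The concern.** The two conditions do not cover everyone who can enrol. A patient treated before with SRS or other focal cranial radiotherapy is not free of prior cranial irradiation, so item 2 does not apply. If that patient has not had WBRT, item 3 does not apply either. The only link left is a column heading that is wider than the text it belongs to.

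Reading the heading as the rule exposes a second gap. For the organ rows, the cumulative limit replaces the study-plan cap and is not added to it. If the earlier treatment gave an organ little dose, the cumulative limit can permit more from the study plan than a never-irradiated patient may receive. The normal-brain rows of the same column go the other way: after prior radiotherapy they are equal or tighter. In a dose-escalation trial, what a critical structure may receive should not depend on how each planner resolves such a mismatch.

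**Working it through.** **Formula and check.** For total dose D in n fractions with alpha-beta ratio 3, BED3 = D(1 + D/(3n)). With n = 5 this is D(1 + D/15). It reproduces the BED3 column of Table 1: 27.5, 30, 32.5, 35, 37.5 and 40 Gy give 77.9, 90.0, 102.9, 116.7, 131.3 and 146.7, printed as 78, 90, 103, 117, 131 and 147.

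**Item 2 caps on the BED3 scale, against the cumulative limits.**

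- Brainstem, optic nerve, chiasm: 26(1 + 26/15) = 71.1; limit 90.
- Spinal cord: 22(1 + 22/15) = 54.3; limit 75.
- Globe: 20(1 + 20/15) = 46.7; limit 66.
- Lens, reading 2.5 as Gy: 2.5(1 + 2.5/15) = 2.9; limit 12.

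Each cap lies below its cumulative limit, so with low prior dose the cumulative limit is the looser of the two.

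**Where this could matter.** Section 4.2.9 excludes "Metastases to brain stem, midbrain, pons, or medulla or within 5 mm of the optic apparatus". The 5 mm distance is written for the optic apparatus only, so a target next to the brainstem, but not in it, is eligible. The margins in 3.4.2 add 0.5 mm + 1 mm = 1.5 mm. All six dose levels (27.5 to 40 Gy) exceed 26 Gy, so the brainstem cap can bind in such a patient.

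**Size at the brainstem.** The documents give no prior structure doses, so a single prior fraction d of 0.5 to 6 Gy to the brainstem is assumed. Prior BED3 = d(1 + d/3). The remaining BED3 is B = 90 − prior BED3. The five-fraction study dose that uses up B is D = 7.5(√(1 + 4B/15) − 1).

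| Assumed prior dose (Gy) | Prior BED3 | B | Study dose allowed (Gy) | Item 2 cap (Gy) |
|---|---|---|---|---|
| 0.5 | 0.58 | 89.42 | 29.9 | 26 |
| 1 | 1.33 | 88.67 | 29.7 | 26 |
| 2 | 3.33 | 86.67 | 29.3 | 26 |
| 4 | 9.33 | 80.67 | 28.1 | 26 |
| 6 | 18.00 | 72.00 | 26.2 | 26 |

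The excess over the cap runs from 15% (29.9/26) to 1% (26.2/26).

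**Crossover.** The two rules agree when prior BED3 = 90 − 71.07 = 18.93. As one fraction, d = 1.5(√(1 + 4 × 18.93/3) − 1) = 6.2 Gy. Above that, the cumulative limit is the stricter rule.

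**After full-dose WBRT.** The schedules are assumed, since the documents name none. 20 Gy in 5 fractions has BED3 46.7 and leaves 19.1 Gy for the brainstem. 30 Gy in 10 has BED3 60 and leaves 15.0 Gy. 37.5 Gy in 15 has BED3 68.75 and leaves 11.9 Gy. All are below 26 Gy, so for structures in the WBRT field item 3 is already tighter than the cap.

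**The case against.** The strongest reply is that this is a one-word slip. The column is headed for previous RT, not previous WBRT, and a planner with a prior-SRS patient has no other column to use. That is a fair reading. A reader might infer that these patients have no dose limit at all, and the heading does not support that. It does not, however, restore a study-plan cap in the organ rows.

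Second, the cumulative figures are the protocol's own ceiling. For WBRT given after the study treatment, item 4 says "the constraints listed in Table 3 should be met during the whole brain radiation treatment", and Table 3 repeats the same organ limits. A plan that follows the column therefore never takes total BED3 above what the protocol accepts. This stands, and it is the main reason to rate the point low.

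Third, the case is narrow. It needs a target next to the brainstem, prior focal treatment, and a prior brainstem dose below about 6.2 Gy as one fraction. SRS to a lesion close to such a target may itself have given the brainstem more than that. This also stands.

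Fourth, 3.4.1 item 8 and 7.2.3 provide for plan checks, and 3.4.6 item 1 records maximum point doses. These help, but a check against the written criteria cannot supply a criterion that is not written.

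Finally, section 1.0 describes the population as untreated or resected. Eligibility is set in section 4, which bars prior cranial radiotherapy only through 4.2.1, and item 3 itself provides for earlier WBRT.

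**Conclusion.** The point holds and is minor. The text of 3.4.6 omits an eligible group. The table column that most likely applies to that group can allow the brainstem 29.9 to 26.2 Gy from the study plan, against 26 Gy with no prior irradiation. This rests on an assumed prior single-fraction brainstem dose of 0.5 to 6 Gy, five study fractions and the protocol's alpha-beta ratio of 3. How many of the 24 patients would be affected is not known, and no effect on DLT rate or MTD is claimed.

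Four stronger readings go beyond the documents:

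- *Later WBRT.* A reader might infer that a plan taken to the ceiling spoils a later WBRT course. Prior-SRS patients cannot be assumed to be WBRT-naive, since section 1.0 describes SRS as salvage after WBRT. Keeping the cap would also secure little: the whole margin of 18.93 is about three fractions of 3 Gy (BED3 of 6 each), whereas an assumed 30 Gy in 10 needs 60.
- *Other organs.* The cord, globe and lens limits show the same ordering, but nothing in the documents shows how those caps would come to bind for the targets treated here. For the optic structures, 4.2.9 already keeps the metastasis away.
- *No brainstem sparing.* With little prior dose, this could be said only of levels −1 and 0 (BED3 78 and 90). At levels 1 to 4 (103 to 147) the limit of 90 still forces sparing.
- *Patients with previous WBRT.* The looser rule is not a general problem for them, because structures given full dose are already held below the cap.

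**What to change.** In 3.4.6 item 3, replace the condition of previous WBRT with any previous cranial irradiation (WBRT, SRS or other). Add one sentence: after prior SRS or other focal radiotherapy, the study plan must meet both the item 2 current-plan maximum dose and the cumulative BED3 limit for each organ row of Table 2, with the stricter one binding. The normal-brain rows can stay as they are.

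The cost is one phrase and one sentence, and slightly tighter planning for a few patients, who would then meet the same caps as those never irradiated. Sample size, dose levels and analysis do not change.
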